3.3.4 Removal of subjects from therapy or assessments

3.3.4.1 Removal of individual subjects

An individual subject is to be removed from the trial if:

1. The subject withdraws consent for trial treatment or trial participation, without the need to justify the decision
2. The subject needs to take concomitant drugs that interfere with the investigational product or other trial medication
3. The subject is no longer able to participate for other medical reasons (such as surgery, adverse events (AEs), or diseases)
4. The subject shows an elevation of AST and/or ALT ≥ 3 -fold ULN combined with an elevation of total bilirubin ≥ 2 -fold ULN (measured in the same blood sample) and/or needs to be followed up according to the 'DILI checklist' provided in the ISF.

In addition to these criteria, the physician may discontinue subjects at any time based on his or her clinical judgment.

A subject can also be removed from the trial if eligibility criteria are being violated or if the subject fails to comply with the protocol (for instance, by non-adherence to dietary rules, or non-attendance at study assessments).

If a subject is removed from or withdraws from the trial prior to administration of trial medication, the data of this subject will not be entered in the case report form (CRF) or trial database and will not be reported in the clinical trial report (CTR).

If a subject is removed from or withdraws from the trial after first administration of trial medication, this will be documented and the reason for discontinuation must be recorded in the CRF. In this case, the data will be included in the CRF/trial database and will be reported in the CTR. At the time of discontinuation a complete end of trial examination will be performed if possible and the information will be recorded in the CRFs. These discontinuations will be discussed in the CTR.

3.3.4.2 Discontinuation of the trial by the sponsor

Boehringer Ingelheim reserves the right to discontinue the trial overall or at a particular trial site at any time for any of the following reasons:

1. New toxicological findings or serious adverse events invalidate the earlier positive benefit-risk assessment. More specifically, the trial will be terminated if more than 50% of the actively dosed subjects at one dose level show drug-related and clinically relevant adverse events of moderate or severe intensity, or if at least one drug-related serious adverse event is reported.
2. The expected enrolment goals overall or at a particular trial site are not met
3. Violation of GCP or the CTP by a trial site or investigator, disturbing the appropriate conduct of the trial
4. The sponsor decides to discontinue the further development of the investigational product.
5. Dose escalation will be stopped as soon as at least 2 subjects at one dose level on active drug showed relevant individual QT prolongation, i.e. absolute QT or QTc greater than 500 ms which has been confirmed by a repeat ECG recording or a QTc increase of greater 60 ms from baseline in connection with absolute QT or QTc greater than 500 ms, which has been confirmed by a repeat ECG recording.

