The 2nd cohort will be treated not earlier than 22 hours later (minimum time interval between 1st subject of 1st cohort and 1st subject of 2nd cohort). In the 2nd cohort, a time interval of at least 10 min will be maintained between dosings of individual subjects (active – active).

The 3rd cohort will be treated not earlier than 46 hours later (minimum time interval between 1st subject of 2nd cohort and 1st subject of 3rd cohort). In the 3rd cohort, a time interval of at least 10 min will be maintained between dosings of individual subjects (3 active, 1 placebo; randomized order).

The dose groups of the SRD part will be investigated consecutively in ascending order of dose

The decision to proceed to the next dose group will be based upon the safety, tolerability, and pharmacokinetic data of the preceding dose groups. The next dose will only be given if, in the opinion of the investigator and the trial clinical monitor (or authorised deputies), no safety concerns arose in the preceding dose group (i.e. no dose-limiting events occurred) and if none of the pre-specified trial-specific stopping criteria were met (refer to [Section 3.3.4.2](#)).

A documented Safety Review must take place prior to each dose escalation. Furthermore, an unscheduled safety review meeting can be requested anytime for any reasonable cause by the Principal Investigator (or an authorised deputy) or the Sponsor of the study, e.g. because of any unforeseen adverse events, etc. Dose escalation will only be permitted if no safety concerns exist in the opinion of the Principal Investigator (or an authorised deputy) and the trial clinical monitor (or an authorised deputy).

The investigator is allowed to alter the scheduled dose levels (e.g. add low and/or intermediate dose levels) on the basis of experience gained during the study, provided the planned and approved highest dose is not exceeded. In this case, the total number of subjects in this trial might increase. The investigator and/or the sponsor should stop dose escalation in case the safety evaluation leads to concerns that would not allow higher dosing.

An overview of all relevant trial activities is provided in the [Flow Chart](#). For visit schedules and details of trial procedures at selected visits, refer to [Sections 6.1](#) and [6.2](#), respectively.

Rel BA part

A total of 12 healthy male subjects is planned to participate in the rel BA trial part.

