The rel BA trial part will be started (i.e., dosing in rel BA part will be started) after availability of preliminary PK and safety data of the 70 mg dose group of the SRD trial part.

The rel BA part consists of three treatment periods, and all entered subjects are planned to participate at all three treatment periods. Treatments are open-label. In periods 1 and 2, the subjects will receive the treatments X (one single dose of 10 mg BI 894416, tablet formulation, fasting conditions) and Y (one single dose of 10 mg BI 894416, oral solution formulation, fasting conditions) in a randomized two-way crossover fashion. These two periods are followed, after documented review of PK and safety data of periods 1 and 2 of the rel BA part, by treatment Z (one single dose of 40 mg BI 894416, tablet formulation, fasting conditions).

The subjects will be randomly allocated to the two treatment sequences (X-Y-Z or Y-X-Z).

The decision to start treatment in the rel BA part (i.e. to administer treatment in period 1) will be based upon the safety, tolerability, and pharmacokinetic data of the available dose groups of the SRD part including also the 70 mg dose group.

The decision to administer treatment in period 3 of the rel BA part will be based upon the safety, tolerability, and pharmacokinetic data of the SRD part including also the 70 mg dose group and of periods 1 and 2 of the rel BA part.

Proprietary confidential information © 2018 Boehringer Ingelheim International GmbH or one or more of its affiliated companies

Treatment in the rel BA part (i.e. treatment in period 1) will only be started if, in the opinion of the investigator and the trial clinical monitor (or authorised deputies), no safety concerns arose in the preceding dose groups of the SRD part (i.e. no dose-limiting events occurred) and if none of the pre-specified trial-specific stopping criteria were met (refer to [Section 3.3.4.2](#)).

Treatment in period 3 of the rel BA part will only be started if, in the opinion of the investigator and the trial clinical monitor (or authorised deputies), no safety concerns arose in the preceding dose groups of the SRD part or in periods 1 and 2 of the rel BA part (i.e. no dose-limiting events occurred) and if none of the pre-specified trial-specific stopping criteria were met (refer to [Section 3.3.4.2](#)).

If it is decided, based on the criteria above, that treatment in period 3 is not given, no further procedures in period 3 are to be done;

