A documented Safety Review must take place prior to starting treatment in the rel BA part in periods 1 and 3. Furthermore, an unscheduled safety review meeting can be requested anytime for any reasonable cause by the Principal Investigator (or an authorised deputy) or the Sponsor of the study, e.g. because of any unforeseen adverse events, etc. Treatments will only be started if no safety concerns exist in the opinion of the Principal Investigator (or an authorised deputy) and the trial clinical monitor (or an authorised deputy).

The investigator and/or the sponsor should decide to stop treatment of subjects in the rel BA part in case the safety evaluation leads to concerns.

An overview of all relevant trial activities is provided in the [Flow Chart](#). For visit schedules and details of trial procedures at selected visits, refer to [Sections 6.1](#) and [6.2](#), respectively.

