3.3.3 Exclusion criteria

Subjects will not be allowed to participate if any of the following general criteria apply:

1. Any finding in the medical examination (including BP, PR or ECG and including the neurological examination) is deviating from normal and judged as clinically relevant by the investigator
2. Repeated measurement of systolic blood pressure outside the range of 90 to 140 mmHg, diastolic blood pressure outside the range of 50 to 90 mmHg, or pulse rate outside the range of 50 to 90 bpm
3. Any laboratory value outside the reference range that the investigator considers to be of clinical relevance
4. Any evidence of a concomitant disease judged as clinically relevant by the investigator
5. Gastrointestinal, hepatic, renal, respiratory, cardiovascular, metabolic, immunological or hormonal disorders

Proprietary confidential information © 2018 Boehringer Ingelheim International GmbH or one or more of its affiliated companies

6. Cholecystectomy and/or surgery of the gastrointestinal tract that could interfere with the pharmacokinetics of the trial medication (except appendectomy and simple hernia repair)
7. Diseases of the central nervous system (including but not limited to any kind of seizures or stroke), and other relevant neurological or psychiatric disorders
8. History of relevant orthostatic hypotension, fainting spells, or blackouts
9. Chronic or relevant acute infections
10. History of relevant allergy or hypersensitivity (including allergy to the trial medication or its excipients)
11. Use of drugs within 30 days prior to administration of trial medication if that might reasonably influence the results of the trial (incl. QT/QTc interval prolongation)
12. Participation in another trial where an investigational drug has been administered within 60 days prior to planned administration of trial medication, or current participation in another trial involving administration of investigational drug
13. Smoker (more than 10 cigarettes or 3 cigars or 3 pipes per day);
14. Inability to refrain from smoking on specified trial days
15. Alcohol abuse (consumption of more than 30 g per day)
16. Drug abuse or positive drug screening
17. Blood donation of more than 100 mL within 30 days prior to administration of trial medication or intended donation during the trial
18. Intention to perform excessive physical activities within one week prior to administration of trial medication or during the trial

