Laboratory data will be compared to their reference ranges. Values outside the reference range as well as values defined as clinically relevant will be highlighted in the listings. Additionally, differences from baseline will be evaluated.

Vital signs or other safety-relevant data observed at screening, baseline, during the course of the trial and at the end-of-trial evaluation will be assessed with regard to possible changes compared to findings before start of treatment.

The ECG variables QT, HR, QTcF, QTcB, PR, QRS, and RR obtained from the centralised evaluation of 12-lead ECG recordings will be the basis for the derivation of quantitative and categorical ECG endpoints for the SRD part. These endpoints and their analyses will be described in the TSAP.

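### Does the second limb of the QT stopping criterion, which repeats the 500 ms condition of the first, leave the escalation rule defective?

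*Protocol*

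**What the plan says.** Protocol Section 3.3.4.2, item 5, counts actively dosed subjects with relevant individual QT prolongation at a dose level and stops escalation when there are two or more. A subject counts in either of two ways:

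- Limb 1: "absolute QT or QTc greater than 500 ms which has been confirmed by a repeat ECG recording".
- Limb 2: "a QTc increase of greater 60 ms from baseline in connection with absolute QT or QTc greater than 500 ms", followed by a clause requiring confirmation on a repeat ECG.

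Protocol Section 3.1 makes the Section 3.3.4.2 criteria a condition for going on. In the single rising dose (SRD) part the next dose is given only "if none of the pre-specified trial-specific stopping criteria were met" and, separately, only if the investigator and the trial clinical monitor see no safety concern. The same pair of conditions applies to the start of the relative bioavailability (rel BA) part and to its third period ("Treatment in period 3 of the rel BA part will only be started if" introduces the latter). Section 3.1 also states "A documented Safety Review must take place prior to each dose escalation" and, for the rel BA part, "A documented Safety Review must take place prior to starting treatment in the rel BA part in periods 1 and 3".

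**The concern.** A criterion of the form 'A, or A together with something else' reduces to A. A reader who sees a rise of more than 60 ms named after the word 'or' expects a second, separate route to stopping. Limb 2 does not provide one, because the 500 ms condition is repeated inside it. That raises the question whether a change-from-baseline trigger was meant and lost in drafting.

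The confirmation clause adds a second doubt. In limb 2 it could refer to the 500 ms value, the rise, both, or either. Two careful readers might then classify the same subject differently. Six subjects per dose group are planned on active drug and the rule acts at two, so one such subject could in principle decide whether escalation stops. In a first-in-man trial, a pre-specified stopping criterion should be read the same way by everyone who applies it.

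**Working it through.** The plan gives no figure to reproduce, so the check is one of logic.

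**Inputs.** All come from Protocol Section 3.3.4.2, item 5. For the first and the repeat ECG, let a1 and a2 mean QT or QTc above 500 ms, and let d1 and d2 mean a QTc rise above 60 ms from baseline. Four yes/no conditions give 2^4 = 16 patterns.

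**Limb 1** is a1 and a2. With d1 and d2 free, it holds in 2 x 2 = 4 patterns.

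**Limb 2** always needs a1 and d1. The rest depends on what the repeat must confirm:

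| What the repeat ECG confirms | Condition | Patterns meeting limb 2 | Of these, outside limb 1 | Patterns meeting item 5 |
|---|---|---|---|---|
| The whole combination | a1, d1, a2, d2 | 1 | 0 | 4 |
| Only the value above 500 ms | a1, d1, a2 | 2 | 0 | 4 |
| Only the rise above 60 ms | a1, d1, d2 | 2 | 1 | 5 |
| Either element | a1, d1, and (a2 or d2) | 3 | 1 | 5 |

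The single extra pattern is the same in the last two rows: a1 = 1, d1 = 1, a2 = 0, d2 = 1. The first ECG shows both features; the repeat still shows the rise but is no longer above 500 ms.

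**Which reading is natural.** The nearest thing the confirmation clause can refer to is the 500 ms value. The comma before the clause favours the whole combination. Both readings give zero extra patterns.

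**When the reading could change a decision.** Let n1 be the number of active subjects at a dose level who meet limb 1, and nx the number in the extra pattern. The choice of reading matters only if n1 is 0 or 1 and n1 + nx is at least 2. With n1 = 1, one subject in the extra pattern is enough; with n1 = 0, two are needed. The 16 patterns are not equally likely, so the counts say which cases exist and nothing about how often they occur.

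**What no reading does.** Limb 2 requires a1 in every row. A rise above 60 ms with QT and QTc never above 500 ms therefore does not meet item 5 under any reading.

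**Several QT measures.** Protocol Section 7.3.3 treats QT, QTcF and QTcB as separate variables ("The ECG variables QT, HR, QTcF, QTcB, PR, QRS, and RR obtained from the centralised evaluation"). Which of them passes 500 ms depends on heart rate and correction formula. Both limbs use the same 500 ms condition, so this shifts how often either is met and leaves the containment as it is.

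**The case for a change.** The strongest case for a change is that either explanation of limb 2 calls for an edit. If it is meant to add nothing, it is surplus text in a stopping rule. If it is meant to add something, the words do not deliver it, apart from one narrow pattern that depends on an unstated reading. The safety review works on judgement and does not repair the wording of a pre-specified criterion. The edit would be one sentence, with no new ECGs, visits or analyses.

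The logical part of this stands: limb 2 is contained in limb 1 on the natural readings, and the text in this copy does not say what the repeat must confirm. The step from there to a defect does not stand, for four reasons.

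- Redundancy is not contradiction. The two limbs never give opposite answers for the same subject, since meeting either one is enough.
- Nothing in the documents shows that a separate change-from-baseline trigger was planned. Writing one in would choose a clinical rule for the sponsor, which a statistical review should not do.
- Other provisions act on every reading. The no-safety-concern condition in Section 3.1 is mandatory. Under Section 5.2.2.2, ECG changes judged clinically relevant are recorded as adverse events, and these feed item 1 of Section 3.3.4.2. Section 3.3.4.1 lets the physician discontinue a subject, and Section 4.1.5.1 foresees an interim safety analysis of ECG data if required. A subject in the extra pattern has already had one ECG above 500 ms, which would be before the people making the decision.
- Protocol Sections 5.2.3 to 5.2.5, cited in Sections 6.2.1 and 6.2.3 for ECG among other procedures, and most of SAP Section 7.8.4 are not in this public copy. The confirmation procedure may be described there.

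**Conclusion.** No change to the plan follows. On the natural reading item 5 has one operative trigger: at least two active subjects at a dose level with a confirmed QT or QTc above 500 ms. Limb 2 then adds 0 of 16 patterns, and removing it would change no escalation decision. On the less natural readings it adds 1 of 16, and that pattern matters only when such a subject is needed to reach the count of two. No endpoint, sample size or analysis is affected.

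This rests on reading item 5 as printed and on the documents showing no separate trigger. Whether a QTc rise alone should count is a medical decision for the sponsor, and no view on it is taken here. What remains is a drafting clarification: how the two limbs relate and which measurement the repeat ECG confirms. The sponsor can settle that, or point to the ECG sections absent from this copy, whenever the section is next revised.

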3.3.5 Replacement of subjects

In case that one dose group in the SRD part of this trial is completed by less than 4 subjects on active treatment (due to e.g. drop-outs or recruitment reasons), or in case that the rel BA part of this trial is completed by less than 8 subjects (due to e.g. drop-outs or recruitment reasons) the trial clinical monitor together with the trial pharmacokineticist and the trial statistician are to decide if and how many subjects will be replaced. A replacement subject will be assigned a unique study subject number, and will be assigned to the same treatment or treatment sequence as the subject he replaces.

4. TREATMENTS

4.1 TREATMENTS TO BE ADMINISTERED

The investigational products have been manufactured by BI Pharma GmbH & Co. KG.

4.1.1 Identity of BI investigational product and comparator products

SRD part

The characteristics of the test product are given below:

Substance: BI 894416

Pharmaceutical formulation: Powder for oral solution

Source: BI Pharma GmbH & Co. KG, Germany

Posology: 1-0-0

Route of administration: p.o.

Duration of use: Single dose

Rel BA part

The characteristics of the test product of the rel BA part are given below:

Substance: BI 894416
Pharmaceutical formulation: Tablet
Source: BI Pharma GmbH & Co. KG, Germany
Unit strength: 10 mg
Posology: - 1-0-0 (treatment X) *and*
- 4-0-0 (treatment Z)
Route of administration: p.o.
Duration of use: One single dose per treatment

The characteristics of the reference product of the rel BA part are given below:

Substance: BI 894416
Pharmaceutical formulation: Powder for oral solution
Source: BI Pharma GmbH & Co. KG, Germany

Posology: (10 mg) -0-0 (treatment Y)
Route of administration: p.o.
Duration of use: Single dose

4.1.2 Method of assigning subjects to treatment groups

Prior to the screening visit, subjects will be contacted in writing and informed about the planned visit dates.

The subjects willing to participate in the SRD part will be recruited to dose groups and cohorts according to their temporal availability. As soon as enough subjects have been allocated to 1 of the dose cohorts (3 cohorts per dose group), the following subjects will be allocated to one of the other dose cohorts. Therefore, the allocation of subjects to dose cohorts is not influenced by trial personnel, but only by the subjects' temporal availability. As the study includes healthy subjects from a homogenous population, relevant imbalances between the dose groups are not expected.

The randomisation list with study subject numbers and allocated treatments (SRD part) or treatment sequences (rel BA part) will be provided to the trial site in advance. The allocation of subjects to study subject numbers will be performed prior to the first administration of trial medication. For this purpose, the subjects will be allocated to a study subject number by drawing lots. Once a subject number has been assigned, it cannot be reassigned to any other subject.

The randomisation procedure is described in [Section 7.5](#).

4.1.4 Drug assignment and administration of doses for each subject

The treatments to be evaluated are outlined in [Table 4.1.4: 1](#) (SRD part) and [4.1.4: 2](#) (rel BA part) below. The dose volume for placebo in the SRD part corresponds to the dose volume of the respective dose level.

The oral solutions for dosing (active drug and placebo) will be prepared according to the instruction given in [Appendix 10.1](#) by pharmacists or qualified pharmacy staff members or qualified medical study personnel at the trial site under the responsibility of the investigator.

The trial medication will be administered to the subjects, while in a sitting or standing position, as an oral dose together with about 240 mL of water under supervision of the investigating physician or an authorised designee. The so-called four-eye principle (two-person rule) should be applied for administration of trial medication and – if applicable – its preparation (e.g. reconstitution), if correct dosage cannot be ensured otherwise.

Administration will be performed following an overnight fast, which is to start no later than 10 h before the scheduled dosing.

4.1.5 Blinding and procedures for unblinding

4.1.5.1 Blinding

The treatments administered in the SRD part (active or placebo) will be single-blind (that is, subjects will not know whether they receive active treatment or placebo). However, the current dose level will be known to the subjects. Treatments of the rel BA part will be open-label because the treatments are distinguishable from each other, and because knowledge of treatment is not expected to influence PK parameters.

For SRD part: Within the central ECG lab, the staff involved with interval measurements will be blinded with respect to the treatment and also with regard to the recording date and time as well as planned time points of the ECGs. The interval measurements for a given subject will be performed in a random and blinded sequence by a single technician.

For SRD part: If an interim safety analysis of ECG data is required, a part of the staff of the central ECG lab may be unblinded. This part of the staff will be strictly separated from the blinded staff members who are involved with ECG interval measurements and assessments of ECGs.

Furthermore, the trial bioanalyst, the trial biomarker analyst, the drug metabolism scientist and trial pharmacokineticist may receive the randomisation codes to perform the preliminary PK analysis. He or she will confirm in writing that the codes will be treated confidentially.

The database of this trial will be handled open-label, because no bias with regard to data cleaning of safety measures is expected.

